### *Milk test*

During the week before the milk test, subjects will fill a food diary. Moreover they will be instructed to not drink any milk, dairy product and any food product containing milk proteins during the 2 days before the milk test. On the day of the milk test, fasting subjects will fill out questionnaires about their actual appetite and GI symptoms, baseline urine and blood samples will be collected, and fasting glycaemia by finger-prick will be measured (time 0). Subsequently, subjects will drink 250 ml of milk within 10 min and thereafter, glycaemia, symptoms and appetite questionnaires, as well as blood samples and urine will be collected at specific time points (time 0.5, 1, 2, 4 and 6 hours after milk ingestion). After the last blood drawing, subjects will be offered lunch and, before leaving the study centre, they will be instructed to fill out GI symptoms and appetite questionnaires, to collect urine, to

fill out a 1-day food diary, and to consume a fixed dinner. Questionnaires, diaries and 6-24h urine samples will be delivered to the laboratory on the next day.

Blood samples will be centrifuged at 4°C and 4000 rpm; serum, plasma and plasma + aprotinin samples will be aliquoted and stored at -40°C.

Plasma samples will be analyzed for:

- casein digestion-derived peptides (beta-casomorphins and all known peptides derived from milk proteins);
- aminoacid profile;
- endocannabinoids and N-acyl-ethanolamines (ECs).

Plasma samples added with aprotinin will be analyzed for:

- gastro-intestinal hormones (in plasma samples pre-treated with aprotinin): insulin, GIP, GLP-1, glucagon, c-peptide, ghrelin, leptin.

Serum samples will be analyzed for:

- DPPIV activity;
- baseline DPPIV concentration.

In urine samples, aliquoted (1.5 ml) and frozen at -40°C, all the following analytes will be measured:

- lactose excretion levels;
- galactose + glucose excretion levels;
- indican excretion levels;
- baseline creatinine concentration.

Subjects will be also asked to collect a fecal sample under usual dietary habits and to fill out questionnaires as follows:

- physical activity questionnaire (short version of the IPAQ);
- questionnaire on quality of life;
- questionnaire on depression, anxiety and stress (DASS);
- semi-quantitative food frequency questionnaire (FFQ);
- the King's Stool Chart, to evaluate frequency and consistency of feces;
- Three Factor Eating Questionnaire (TFEQ) to evaluate individual eating behaviour.

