## Statistical analysis plan

### Sample size calculation

The sample size for this study has been calculated on the basis of the primary endpoints here listed:

- milk-derived peptides plasma concentrations after milk consumption;
- lactose urinary excretion after milk consumption;
- post-prandial plasma profile of GI hormones and ECs.

Considering circulating mean values and standard deviations reported by Deth et al. (2016) in blood of healthy population, power analysis indicated that a sample size of 19 participants per group is sufficient to detect a minimum variation of 40% in circulating BCM-7 with a power of 80% and an  $\alpha = 0.05$ .

Considering excreted % of lactose in urine, hydrogen concentration in breath and relative standard deviations as reported by Bezerra et al. (1990) a sample size of 19 participants per group is sufficient to detect a 15% minimum variation of lactose and a 50% minimum variation of hydrogen in healthy subjects, with a power of 80% and an  $\alpha = 0.05$ .

Regarding post-prandial plasma profile of GI hormones and ECs, our previous studies showed that a sample size of 13 participants is adequate to find significant differences with an 80% power and an  $\alpha = 0.05$ . (Mennella et al., 2015; Mennella et al., 2016).

The participant number will be increased up to 40 (20 subjects per group) in view of possible dropouts.

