### Statistical analysis

Data will be expressed as means  $\pm$  SEMs, unless otherwise specified.

Two-tailed P values lower than 0.05 were considered significantly different

Missing data will be handled as such, i.e., no imputation of missing data will be performed.

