### *Continuous variables with repeated measures*

Normality of measures, for each time, will be assessed using the Shapiro-Wilk test.

Differences of variables between baseline and over time within and between the groups, for normally distributed variables, will be tested by ANOVA with repeated measures on one factor (time) and Bonferroni adjustment for multiple comparisons. For non-normally distributed variables, Friedman test and pairwise Wilcoxon as a *post hoc* test will be applied.

Analysis of quartiles will be performed for both baseline values and pairwise time points ( $\Delta$ ) upon milk ingestion.

For these variables with repeated measures, the total area under the curves (AUCs) will be also estimated using the linear trapezoidal rule, and differences in AUCs between the groups will be assessed by proper parametric or non-parametric analyses including as covariates the potential confounding variables measured at baseline.

Pearson's correlation coefficients will be calculated to assess bivariate associations among continuous variables at baseline or partial associations of estimated AUCs controlling for baseline values for variables with repeated measures.

Spearman's rank correlation will be used to assess association between non-parametric variables collected and microbiota related variables (e. g. species abundance and genes abundance).

In order to explore differences in microbiome profiles, a Partial Least Squares Discriminant Analysis was applied.

Furthermore, principal component analyses (PCA) on specific variables at baseline or unstandardised residuals correlation between AUCs and related baseline values will be also performed in order to extract features relevant to the cluster structure. Moreover, statistical significance of the distance between groups in the PCA analysis will be computed using the Hotelling T2 test.

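### No multiplicity adjustment is stated for the pairwise Wilcoxon tests after Friedman, although the parallel ANOVA branch has one

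*Combined protocol and SAP*

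**What the plan says.** The section on continuous variables with repeated measures has two branches, chosen by a Shapiro-Wilk test at each time.

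- Normal variables: "ANOVA with repeated measures on one factor (time) and Bonferroni adjustment for multiple comparisons".
- Other variables: "For non-normally distributed variables, Friedman test and pairwise Wilcoxon as a" post hoc test. No adjustment is named.

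The scope of both branches is "Differences of variables between baseline and over time within and between the groups", so the tests are not limited to contrasts with the fasting value. The opening of the Statistical analysis section sets one threshold for everything: "Two-tailed P values lower than 0.05 were considered significantly different". No other part of the plan mentions multiplicity.

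The Milk test section fixes the blood sampling times: a fasting sample at time 0, then "time 0.5, 1, 2, 4 and 6 hours after milk ingestion".

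**The concern.** The two branches answer the same question, at which times an analyte changes after milk, but only one states control of the error rate over the many pairs. Which branch an analyte enters depends on a normality test in about 20 subjects per group. Two similar hormones could therefore be reported under quite different error rates, and a reader of the plan could not tell.

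The Friedman test does not close the gap. It is a test that all times are equal. Once one real postprandial peak makes it significant, every pair among the unchanged times is tested at 0.05 with nothing in front of it. Some change after milk is what the trial expects, since the plasma responses of peptides, GI hormones and endocannabinoids are primary objectives. At stake is the description of the postprandial profile: a time point could be reported as a change when it is not one.

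**Working it through.** The plan states no error rate for these follow-up tests, so it has no figure of its own to reproduce. Its sample size enters only as n. The 19 per group cannot be re-derived, because the mean and SD are not given, and nothing below depends on it.

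**Inputs from the documents**
- Six blood sampling times: 0, 0.5, 1, 2, 4 and 6 h (Milk test).
- Two-tailed 0.05 for each test (Statistical analysis).
- 20 subjects per group, 40 in all (Sample size calculation: "The participant number will be increased up to 40 (20 subjects per group) in view of possible dropouts"). n = 40 applies only if the groups are pooled.

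**Assumptions, because the documents give none:** size and shape of the curve, distribution, and correlation between times. The pairwise Wilcoxon tests are read as signed-rank tests.

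**Step 1, pairs.** 6 × 5 / 2 = 15 per analyte and group.

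**Step 2, null pairs.** If m times are raised to distinct levels and the rest are equal, (6 − m)(5 − m)/2 pairs are truly null: 10 for m = 1, 6 for m = 2, 3 for m = 3, 1 for m = 4.

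**Step 3, reference.** If 10 null tests were independent, the chance of at least one false result would be 1 − 0.95^10 = 0.401. The pairs share time points and are correlated, so the true figure is lower and was simulated.

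**Step 4, simulation of the procedure as written.** Friedman at 0.05; if significant, all 15 signed-rank tests at 0.05; count runs with at least one rejection among the null pairs. Between 1,500 and 20,000 runs per setting.

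| Assumed truth | At least one false pair |
|---|---|
| No change at any time | about 4-6% (34-41% without the Friedman gate) |
| One time clearly raised | about 24-32% |
| Two raised | about 18-24% |
| Three raised | about 12-13% |
| Four raised | about 4-5% |
| One raised, only contrasts with time 0 tested | about 14-17% |

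The 24-32% comes from lognormal data, shifts of 0.7 or 1.5 SD, n = 20 or 40, and correlation 0.3-0.6. The central case (n = 20, lognormal, 1.5 SD) gives 30.0% with no correlation and 30.8% with correlation 0.5. Other settings with a peak of at least 1 SD give 26-33%, or about 25-28% where correlation decays slowly over time. With normal data and a weak peak (0.5-0.7 SD), the Friedman test was significant in only 23-78% of runs and the rate was about 13-27%.

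**Step 5, with adjustment, one raised time.**
- Bonferroni over 15 pairs tests each at 0.05/15 = 0.0033. With 10 null pairs the bound is 10 × 0.0033 = 0.033; simulated, about 2-3%.
- Holm is bounded by 0.05; simulated, about 3-5%.

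**Step 6, both groups.** If both groups have one raised time, the chance of a false pair in at least one of them is 1 − (1 − 0.24)² = 0.42 to 1 − (1 − 0.32)² = 0.54 for a single analyte.

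**The case against.** The strongest reply is that the largest figure belongs to the curve shape with the most null pairs. A postprandial curve may well rise and fall over several times, and with four raised times the rate is back near 5%. This stands, and it is why the result is given as a range by curve shape.

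Several stronger readings are tempting, and the documents do not support them:

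- *That skewed analytes in general are affected.* The section on continuous variables first applies logarithmic, square-root or other transformations. Only variables still non-normal afterwards reach this branch, and how many will do so is unknown. Lognormal data should be rescued by the log step. The error rate does not hinge on that choice, however: heavy-tailed (t with 3 degrees of freedom) data at n = 40 gave 29.6-30.8%.
- *That the comparison of the two consumer groups is inflated.* The affected tests are within-subject time contrasts. The between-group comparison of AUCs is a separate analysis and is not touched.
- *That the authors decided to test unadjusted.* The plan only fails to state an adjustment. The sentence before suggests that one is wanted, so this may be a drafting omission. An adjustment applied at analysis would remove the inflation, but the plan does not commit to it.
- *That 15 pairs applies to every repeated measure.* It fits the blood samples. Questionnaires and urine collection continue after 6 h, so their count differs.
- *That Bonferroni in the ANOVA branch should be replaced.* It is valid and prespecified. Preferring Holm there would correct no error.

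**Conclusion.** The point holds in limited form. Followed literally, the non-parametric branch lets the chance of a false time difference rise above 5% for most of the curve shapes examined, to about a quarter to a third when a single time is clearly raised. The parallel branch is adjusted. These rates are per analyte and per analysed group. They assume that all 15 pairs are tested (unless stated otherwise) and that the real change is large enough for the Friedman test to reject. The textual gap is certain; its size rests on assumed curves. It is worth correcting because the affected measures include primary ones and the remedy is trivial, but it does not undermine the trial's comparison between groups.

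**What to change.** Add one sentence to the section on continuous variables with repeated measures:

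- the pairwise Wilcoxon P values are adjusted within each analyte, by Holm, or by Bonferroni to match the ANOVA branch; and
- the family is named: either all pairs of times or only those against time 0. For the blood measures that is 15 or five pairs; with five, the Bonferroni threshold is 0.05/5 = 0.01.

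The choice of family should be made before the data are seen. The ANOVA branch needs no change. No extra data or subjects are needed. The price is that fewer pairs will be reported as significant.

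### For a primary plasma analyte treated as normal, HMC and NHMC are compared by both repeated-measures ANOVA and AUC with neither named as deciding, so the 5% error rate becomes about 9–13% under assumed correlations

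*Combined protocol and SAP*

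**What the plan says.** The Objectives and the Sample size calculation give the primary plasma endpoints as responses or profiles, for example "milk-derived peptides plasma concentrations after milk consumption". Blood is drawn at time 0 and at "time 0.5, 1, 2, 4 and 6 hours after milk ingestion", so each analyte yields six values per subject.

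The SAP section *Continuous variables with repeated measures* then plans, for normally distributed variables:

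- a repeated-measures ANOVA for "Differences of variables between baseline and over time within and between the groups", with a Bonferroni adjustment stated in the same sentence;
- a quartile analysis: "Analysis of quartiles will be performed for both baseline values and pairwise time points";
- in addition, a trapezoidal AUC, where "differences in AUCs between the groups will be assessed by proper parametric or non-parametric analyses", with baseline confounders as covariates.

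For non-normal variables the ANOVA is replaced by Friedman and Wilcoxon tests. The AUC comparison remains.

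The general rule in *Statistical analysis* is "Two-tailed P values lower than 0.05 were considered significantly different". No section says which result answers the primary question for an analyte.

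**The concern.** The ANOVA and the AUC comparison can disagree. A group-by-time term can be significant while the AUC is null, or the reverse, and under the plan either could be presented as the primary result. The Bonferroni adjustment covers comparisons inside the ANOVA but not the choice between ANOVA and AUC.

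This is separate from the number of analytes: it would remain if BCM-7 were the only one measured. The stated 5% error rate and 80% power each describe a single two-group comparison, and the plan does not identify which comparison that is.

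**Working it through.** **1. The plan's own figure.** The Sample size calculation states that "a sample size of 19 participants per group is sufficient to detect a minimum variation of 40% in circulating BCM-7", at 80% power and alpha 0.05. The SD is only in a cited source, so the figure can be back-solved but not reproduced:

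d = √[2 × (1.960 + 0.842)² / 19] = √(15.70 / 19) = 0.91, or 0.93 with the t distribution.

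A 40% difference then implies an SD of 40 / 0.91 = 44% of the mean (40 / 0.93 = 43% with t). Whatever the SD, the statement does not say which draw, or which summary of the six draws, it refers to.

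**2. The tests differ.** Trapezoidal weights for draws at 0, 0.5, 1, 2, 4 and 6 h are 0.25, 0.5, 0.75, 1.5, 2 and 1 (sum 6). The AUC therefore puts (1.5 + 2 + 1) / 6 = 75% of its weight on the last three draws. The ANOVA group effect weights all six draws equally, including time 0. The group-by-time term tests whether the profiles differ in shape.

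**3. Reference values.** With k independent tests at 0.05, the chance of at least one false positive is 1 − 0.95^k: 9.8% for k = 2 and 14.3% for k = 3. The tests here are correlated, so simulation is needed.

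**4. Simulation with no true group difference.**

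- From the documents: 20 per group ("The participant number will be increased up to 40 (20 subjects per group) in view of possible dropouts"), six draws, two-sided 0.05.
- Assumed: normal data; the correlations in the table (autoregressive values are per hour); Greenhouse-Geisser correction; Bonferroni over six time points.
- Runs: 20,000 trials per setting.

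The two middle columns give the chance that at least one of these is significant: ANOVA group effect, group-by-time, adjusted time points, AUC.

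| Correlation | AUC unadjusted | AUC adjusted for time 0 | Adjusted AUC as the only test |
|---|---|---|---|
| Compound symmetry 0.3 | 11.7% | 13.1% | 5.1% |
| Compound symmetry 0.5 | 10.9% | 12.9% | 4.9% |
| Compound symmetry 0.7 | 10.1% | 12.5% | 4.8% |
| Compound symmetry 0.9 | 9.0% | 12.1% | 4.9% |
| Autoregressive 0.5 | 12.1% | 13.2% | 5.0% |
| Autoregressive 0.7 | 11.5% | 12.8% | 5.0% |
| Autoregressive 0.9 | 10.4% | 12.4% | 5.2% |

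**5. Sensitivity.**

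- Group-by-time plus AUC only, over five assumed correlation settings: 8.5–9.6%.
- Adding the group effect to those two: 9.8–10.8% with unadjusted AUC, 11.6–12.7% with baseline-adjusted AUC.
- 19 per group (compound symmetry 0.5, 0.7, 0.9): 9.2–11.0% unadjusted, 12.7–12.9% adjusted.
- No sphericity correction, adjusted AUC: 12.9–16.0%.
- Shapiro-Wilk check at each time applied first, failures sent to a single AUC test, no transformation step (4,000 trials per setting): 73–78% of truly normal analytes pass all six checks. The overall rate becomes 9.0–10.3% (unadjusted) or 11.0–11.6% (adjusted).

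**6. Non-parametric branch.** Friedman and Wilcoxon are within-subject tests and do not compare HMC with NHMC, so the AUC is the only clear between-group test. With log-normal data, Mann-Whitney alone gives 4.9–5.0%, Quade alone 4.6–5.1%, and either one 7.1–9.2%.

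**The case against.** The strongest reply is that the plan sets no success criterion. Its primary objectives are to evaluate responses in two non-randomised groups, so a significant route becomes a false claim only if it is reported as the group difference. That is fair: the figures measure the opportunity for a false finding. But the plan calls these endpoints primary and attaches an alpha and a power to them, and both need an identified test.

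Four limits stand:

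- The rates rest on correlations, a sphericity correction, a Bonferroni extent and an AUC covariate that the documents do not give.
- The SAP does not list group effect and group-by-time as separate tests. Counting only group-by-time and AUC gives the low end of the range.
- The baseline covariates may or may not include the analyte's own time-0 value.
- The power statement concerns circulating BCM-7, so naming the AUC does not by itself attach the 80% to it.

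Stronger readings are tempting but not supported:

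- **Every primary analyte at 12–15% or more.** The non-parametric branch has no ANOVA group test. The upper end needs additions such as quartiles of change counted as a group comparison, which the quartile sentence does not say, or a second AUC test, when one AUC comparison is planned.
- **A change in NHMC but not in HMC read as a group difference.** If both groups had the same true change, each detected with power p, exactly one would be significant with probability 2p(1 − p): 50% at p = 0.5, 32% at p = 0.8. The SAP does not say it will argue this way, and p is assumed.
- **The same inflation for urinary lactose.** It was not simulated, and the Sample size calculation already treats it as one quantity, the percentage excreted.

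**Conclusion.** The concern holds for primary plasma analytes treated as normally distributed. At least two between-group routes are planned, each is read at 0.05, and none is named as deciding. The chance of at least one false group difference per analyte is about 9–13%, or 1.8 to 2.6 times the stated 5% (9 / 5 and 13 / 5), given normal data, the assumed correlations and a sphericity correction. On the non-parametric branch the excess disappears if a single AUC test is fixed. None of the limits above supplies the missing deciding contrast. This should be settled before the data are analysed, but it does not call the design into question.

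**What to change.** In *Continuous variables with repeated measures*:

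1. Name one deciding HMC–NHMC contrast per primary plasma analyte: the 0–6 h AUC comparison already planned.
2. Fix its single parametric test, its single non-parametric fallback and the rule for switching. The SAP's own pairs would serve: t test with Mann-Whitney if there are no covariates, ANCOVA with Quade if there are.
3. List the covariates in advance and state whether the time-0 value is one of them. The groups are formed by milk habit and symptoms, so if their time-0 values differ, adjusting for them changes the question. The sponsor should choose and say why.
4. State that ANOVA terms, time-point comparisons, quartile analyses and within-group changes are supportive and cannot establish a group difference on their own.
5. For urinary lactose, name total 0–24 h excretion, in line with the 24 h span in the Objectives.

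In *Sample size calculation*, say which summary of BCM-7 the 40% difference and its SD refer to.

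The cost is SAP wording only: every planned analysis is still run, and one named test brings the simulated rate back to 4.8–5.2% per analyte. The downside is that a difference confined to a short window would be reported only as supportive. The 0.5 h draw, for example, carries 0.5 / 6 = 8% of the AUC weight. The change does not address the number of analytes.

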## **Objectives**

This study aims to compare two groups of healthy (non-lactose intolerant) subjects who are irregular milk consumers, due to milk induced gastrointestinal disorders, with another group of healthy subjects who consume milk regularly, without symptoms, in relation to the primary and secondary objectives here described.

By performing a milk test in which volunteers ingest 250 ml of UHT semi-skimmed milk, primary objectives include the evaluation of:

- plasmatic response of milk-derived peptides;
- plasmatic profile of GI hormones;
- plasmatic profile of endocannabinoids and N-acyl-ethanolamines.
- urinary profile of lactose over 24 h;

Secondary objectives include the assessment of:

- baseline and postprandial plasma profile of aminoacids;
- baseline and postprandial blood glucose;
- baseline and postprandial GI symptoms;
- baseline serum concentration of dipeptidyl peptidase IV (DPPIV);
- baseline and postprandial serum activity of dipeptidyl peptidase IV (DPPIV);
- urinary excretion of indican as marker of protein digestibility;
- correlations of GI symptoms with appetite ratings and blood glucose, plasma GI hormones, plasma peptides and amino acids as well as with urinary excretion of lactose and galactose + glucose;
- the composition of the intestinal microbiota (metagenomic analysis);
- the psychological profile through questionnaires on the perception of quality of life, on levels of depression, anxiety and stress and on eating behavior.

Further secondary objectives include the assessment of:

- the prevalence of lactose malabsorption in the two groups, by using results from Lactose H2 breath test performed during the recruitment procedure;
- urinary excretion of lactulose, mannitol and sucralose as markers of intestinal permeability after an oral challenge of these 3 sugar probes.

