## Allocation

Subjects who will be assessed as eligible and will accept to enter the study protocol, will be allocated in the proper group, and the enrollment will be concluded when 2 groups of subjects will be constituted as follows:

- **Group 1**, habitual milk consumers (HMC): 20 subjects who are regular milk consumers ( $>700$  mL/week), do not experience GI discomforts after milk intake and are lactose tolerant or lactose malabsorber.
- **Group 2**, non-habitual milk consumers (NHMC): 20 subjects who are not regular milk consumers ( $< 150$  mL/week), because of GI discomforts after milk intake and are lactose tolerant or lactose malabsorber.

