Anthropometric data of weight and height will be measured as well.

Fecal samples, stored at -40°C, will be used for DNA extraction according to the standard operating procedures of the International Human Microbiome Consortium (<http://www.human-microbiome.org/>). Statistical analysis will be carried out by the most appropriate methods in order to infer the associations between specific microbiota signatures and clinical, dietary and metabolomic variables.

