#### Continuous variables

Normality of continuous variables will be assessed using the Shapiro-Wilk test. For non-normal variables showing a significant positive skewness, logarithmic, square-root, exponential, or inverse transformation will be applied. For those variables which will not show a normal distribution after arithmetic transformation, non-parametric tests will be used.

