### *Continuous variables without repeated measures*

For those variables which will show a normal distribution at the Shapiro-Wilk test, an independent two-sample T test will be performed to check differences between groups, whereas ANCOVA analysis will be performed to include covariates in the analysis.

Differences between groups of non-normally distributed variables will be assessed by Mann-Whitney U test, while non-parametric analysis of covariance (Quade's test) will be used to explore the effects of any covariates.

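### The symptom-biomarker correlations name no analysis set and no HMC/NHMC term; if pooled, they cannot separate individual-level association from the group contrast

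*Combined protocol and SAP*

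**What the plan says.** The Objectives section of the combined protocol and SAP lists as a secondary objective "correlations of GI symptoms with appetite ratings and blood glucose, plasma GI hormones, plasma peptides and amino acids", and extends this to urinary lactose and galactose plus glucose.

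The method is in the SAP section on continuous variables with repeated measures. It gives Pearson coefficients for variables at baseline, "partial associations of estimated AUCs controlling for baseline values for variables with repeated measures", and Spearman coefficients for non-parametric and microbiota-related variables. I take the baseline values to be each variable's own, because the PCA sentence in the same section pairs AUCs with their related baselines. No other control variable is named, and the section does not say which subjects enter the correlations.

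The Allocation section forms two groups of 20. HMC subjects "do not experience GI discomforts after milk intake". NHMC subjects drink little milk "because of GI discomforts after milk intake".

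**The concern.** One of the two correlated variables, GI symptoms after milk, is close to what defines the groups. If symptom scores in the milk test are higher in NHMC, and an analyte also differs between HMC and NHMC, pooling the groups gives a non-zero correlation even when symptoms and analyte are unrelated among subjects of the same group. If the within-group association has the opposite sign to the group contrast, pooling can cancel it.

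What is at stake is the interpretation of a stated secondary objective. A reader would take a significant symptom-peptide correlation as support for a mechanism acting in individuals. It could instead restate, partly or wholly, the HMC/NHMC comparison already reported elsewhere.

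**Working it through.** **1. Does another section supply the group term?**
- Objectives: "This study aims to compare two groups of healthy" states a general aim. It does not say how group enters a correlation.
- Continuous variables without repeated measures: "ANCOVA analysis will be performed to include covariates in the analysis" belongs to the tests of group differences. So does the covariate clause for AUCs in the repeated-measures section.
- Further analyses: the split that mentions correlations is optional and is by lactose status. Allocation admits lactose tolerant subjects and malabsorbers to both groups, so it does not stand in for HMC/NHMC.

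None supplies it. Because Further analyses offers subgroup correlations as an extra, pooling is the natural reading of the main analysis, but it is not stated.

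**2. The plan's own figure.** The plan gives no power for correlations. Its nearest figure is 19 per group for a 40% variation in BCM-7 (80% power, alpha 0.05). The SD is not in the documents, so 19 cannot be reproduced independently. Solving back:
- Normal approximation: d = (1.960 + 0.842) × √(2/19) = 0.909.
- t test: d = 0.934, which implies an SD of 0.40/0.934 = 43% of the mean.

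I use 0.934 SD as one reference analyte difference. It is the minimum detectable difference, not an expected one.

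**3. Formula.** With equal groups, within-group SD 1, zero within-group correlation, analyte difference dx and symptom difference dy:

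r(pooled) = dx·dy / √[(dx² + 4)(dy² + 4)]

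For dx = 0.934 and dy = 1.5: 1.401 / √(4.872 × 6.25) = 0.254. The critical |r| at n = 40 is 0.312.

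Baseline control removes within-group variance but leaves any group difference that arises only after milk. With a baseline-AUC correlation of 0.5 the residual SD is √(1 − 0.25) = 0.866. The differences become 0.934/0.866 = 1.079 and 1.5/0.866 = 1.732, and r rises to 1.869 / √(5.164 × 7.000) = 0.311.

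**4. Simulation.** Assumptions: 20 per group, zero within-group association, baseline-AUC correlation 0.5, 20,000 runs per scenario. The table gives the percentage of trials significant at two-sided 0.05, with an analyte difference of 0.93 SD.

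| Test | Symptom difference 0.5 SD | 1.0 SD | 1.5 SD | 2.0 SD |
|---|---|---|---|---|
| Partial Pearson, none of the group difference at baseline | 12 | 31 | 51 | 65 |
| Partial Pearson, half at baseline | 7 | 13 | 19 | 24 |
| Spearman, no control | 9 | 23 | 38 | 52 |

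- Partial Pearson with all of the difference at baseline: 5-7%.
- With group added, partial Pearson or partial Spearman: 4.7-5.4%.
- Smaller analyte differences, none at baseline: 0.5 SD gives 8-25% (partial Pearson) and 6-19% (Spearman); 0.3 SD gives 6-12% and 6-10%; zero gives about 5% for every test.
- Symptom scores floored so that about half of HMC score zero (0.93 SD): partial Pearson 11/26/45/62%, Spearman 9/21/37/51%, about 5% with group.
- Baseline-AUC correlation 0.3 or 0.7 (0.93 SD, none at baseline): 11-53% or 20-86%.

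**5. Masking.** With a true within-group residual correlation of −0.4, analyte difference 0.93 SD and symptom difference 1.5 SD (4,000 runs), the baseline-controlled partial r averages 0.06 and is significant in 4% of trials. With group added it averages −0.39 and is significant in 71%.

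**6. Cost of the group term when there is no group difference.** Power goes from 84.9% to 83.9% at a within-group r of 0.45. Under the baseline-adjusted set-up with a residual correlation of 0.4 it goes from 72% to 71%.

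**The case against.** The strongest reply is that the pooled correlation is a legitimate quantity. The objective asks only whether symptoms correlate with analytes, and between-group variation is part of that answer. When both variables differ by group, the pooled correlation is truly non-zero. A reader might infer from the table that the planned test has a false-positive rate of up to 65%. The documents do not support that: the percentages are error rates only for the within-group association, which the plan never names as its target. Group is also a coarse version of the symptom variable, so adjusting for it removes real signal. This stands, and it is why the pooled coefficient should be kept.

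A reader might also infer that the plan prescribes pooling all 40 subjects. It does not. The analysis set is unstated, and correlations run within each group would not have the problem.

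Mixing also needs the milk-test symptom scores to differ by group. Allocation rests on habits and reported discomfort, the correlated score comes from one 250 ml test, and subjects with vomiting or loose stools are excluded. A difference is plausible, but its size is unknown.

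The highest figures take a 0.93 SD analyte difference with none of it at baseline, which is the unfavourable end. Using Spearman for symptom-analyte pairs relies on the general fallback, under which for "variables which will not show a normal distribution after arithmetic transformation, non-parametric tests will be used". The symptom-correlation objective does not list microbiota; the nearest text, the plan to "infer the associations between specific microbiota signatures and clinical, dietary and metabolomic variables", is general.

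These points limit the size and reach of the concern. They do not supply a way to tell the two components apart.

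**Conclusion.** The concern holds in a conditional form. If the correlations are pooled, and both the analyte and the milk-test symptom score differ between HMC and NHMC, the planned coefficient mixes the group contrast with within-group association. It can then suggest an individual-level association that is absent or hide one that is present. Own-baseline control removes the mixing only to the extent that the group difference already exists before milk. Analytes that do not differ by group are unaffected.

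The direction follows from the design. The size rests on assumed differences, and the range of about 5% to 65% applies at a baseline-AUC correlation of 0.5. It would be too strong to call the pooled correlations invalid, or to extend the point to the primary objectives or the sample size. This is a cheap improvement to a secondary analysis that should be made.

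**What to change.** In the SAP section on continuous variables with repeated measures, state the analysis set for the correlations. Add that each pooled symptom-biomarker correlation, and any symptom-microbiota correlation that is made, will be accompanied by a version that also controls for HMC/NHMC group:
- partial Pearson given each variable's own baseline plus group; or
- partial Spearman given group, where the non-parametric fallback applies.

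Label the pooled coefficient as including the between-group contrast, and base any claim of individual-level association on the group-adjusted one. Separate within-group coefficients are optional and descriptive: at n = 20 they need |r| of about 0.44 for significance.

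The cost is one sentence, a variable already recorded, one degree of freedom and about one point of power. The number of tests need not grow if the pooled coefficient is shown without its own p-value, although that does change which test is reported. The real downside is that the adjusted coefficient discards true between-group signal, so both should be shown.
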